9.2 MEASUREMENT OF TREATMENT COMPLIANCE

Dosing compliance for a specified period is defined as the total number of capsules actually taken by a patient during that period divided by the number of capsules that were expected to be taken during the same period multiplied by 100. The total number of capsules actually taken during a specific period is calculated as the number of days in that period multiplied by the number of capsules taken each day during that period. The number of capsules expected to be taken for a specific treatment period will be calculated by multiplying the number of days in that period by the number of capsules to be taken per day. This information will be obtained from the IP record of the patient's eCRF. Descriptive statistics for IP compliance will be presented by treatment for each period between 2 consecutive visits, as well as for the period from the first dose of DB IP actually taken to the last dose of DB IP actually taken from the Safety Population.

Descriptive statistics (n, mean, standard deviation, median, Q1, Q3, minimum and maximum) for OL IP compliance will be presented overall for each period between 2 consecutive visits, as well as for the entire OLTP for the OL Safety Population. Descriptive statistics (n, mean, standard deviation, median, Q1, Q3, minimum and maximum) for DB IP compliance will be presented by treatment group for each period between 2 consecutive visits, as well as for the entire DBTP for the DB Safety Population.

10.0 EFFICACY ANALYSES

All efficacy analyses for the OLTP will be performed using the OL ITT population, unless stated otherwise. Baselines for efficacy parameters in the OLTP will be defined as the last non-missing efficacy assessment before the first dose of OL IP.

All efficacy analyses for the DBTP will be performed using the DB ITT population, unless stated otherwise. Baselines for the additional efficacy parameters in the DBTP will be defined as the last nonmissing efficacy assessment before the first dose of DB IP.

All statistical tests will be 2-sided hypothesis tests performed at the 5% level of significance and all confidence intervals (CIs) will be 2-sided 95% CIs, unless stated otherwise.

To accommodate the flexible duration of the OLTP, the derived visits in the DBTP will be named as Week *i* post randomization (or DB Week *i*) for a specific Week *i* after the first dose of the DB study medications. The total exposure to IPs for patients in Week *i* post randomization will vary because of the flexible OLTP. The detailed week-mapping windows is provided in Section 16.1.

10.1 PRIMARY EFFICACY PARAMETER

The primary efficacy parameter is the time to first relapse during the DBTP, defined as the number of days from the randomization date to the first relapse date. Relapse during the DBTP will be defined as the occurrence of any of the following:

- Increase in PANSS total score by $\geq 30\%$ for patients who had a PANSS total score of ≥ 50 at Randomization/Visit 13 (Week 18) or a ≥ 10 -point increase in PANSS total score for patients who had a PANSS total score < 50 at Randomization/Visit 13 (Week 18)
- Increase in CGI-S score by 2 or more points relative to Randomization/Visit 13 (Week 18)
- Score of > 4 on 1 or more of the following 7 PANSS items: P1: delusions; P2: conceptual disorganization; P3: hallucinatory behavior; P6: suspiciousness/persecution; P7: hostility; G8: uncooperativeness; G14: poor impulse control
- Deliberate self-injury or aggressive/violent behavior

- Initiation of treatment with a mood stabilizer, antidepressant, antipsychotic agent, or with a benzodiazepine that exceeds the protocol-specified allowance or duration (ie, more than 2 mg/d of lorazepam equivalent or for more than 3 consecutive days) to treat worsening symptoms of schizophrenia or any other psychiatric disorder as judged by the clinical impression of the investigator
- Psychiatric hospitalization due to worsening of the patient's underlying condition
- Exacerbation of psychiatric illness as judged by clinical impression of the investigator (e.g., clinically significant agitation, suicidal or homicidal ideations)

Patients who did not meet the above relapse criteria will be censored at the time of completion or discontinuation from the study.

To test the primary null hypotheses that the distribution of the time to first relapse for each of the cariprazine 4.5 mg/d and 3.0 mg/d treatment groups are not different from that for the placebo treatment group, the log-rank test is used to compare the time to relapse between each cariprazine group and placebo group for the DB ITT population. Estimates of the hazard ratio and 95% CIs will be based on the Cox proportional hazards model with treatment group as explanatory variable. The Kaplan-Meier estimates for the cumulative distribution of the relapse rate for each treatment group will be provided.

The fixed-sequence testing procedure will be used for multiple comparisons to control the family-wise Type I error rate at a 0.05 level. The comparison of cariprazine 4.5 mg/d versus placebo for the primary endpoint will be tested first at a 0.05 significance level using the log rank test; the comparison of cariprazine 3.0 mg/d versus placebo will be tested only when the test for cariprazine 4.5 mg/d versus placebo is significant at 0.05 level.

Two sensitivity analyses will be performed to assess the robustness of the primary analysis results to the possible violation of the noninformative censoring assumption. The first sensitivity analysis is delta-adjusted imputation method ([Zhao 2014](#)). The delta-adjusted sensitivity analysis specifies that the hazard of having an event for subjects who discontinued before the timepoint is multiplicatively increased relative to the hazard for subjects who continued beyond the timepoint for the cariprazine treatment group. The second sensitivity analysis is based on the reference-based imputation method ([Lu 2015](#)). The reference-based sensitivity analyses use a sensitivity parameter to characterize the gradual deviation from the noninformative censoring underlying the primary analyses toward the informative censoring, which assumes that the hazard of relapse for cariprazine-treated patients who discontinued is the same as the hazard for relapse for placebo-treated patients. A multiple imputation approach will be used to implement the sensitivity analyses. Details for two sensitivity analyses including SAS codes were provided in [Appendix II](#).

The analysis for the primary efficacy parameter will be performed within each category of the following:

- Age group (< 55 years, \geq 55 years)
- Sex (male, female)
- Race (white, all other races)
- Region (US, Non-US)

SAS codes for planned analyses of the primary efficacy variable were provided in [Appendix I](#) and [Appendix II](#).

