8.8 Early Discontinuation of Subjects

Patients may discontinue from the study at any time for any reason. Discontinuation is permanent; once a patient is discontinued, he/she shall not be allowed to enroll again.

Patients can be prematurely discontinued for one of the following reasons:

- AE

- Noncompliance with protocol
- Noncompliance with IP dosing regimen
- Withdrawal of consent (a clear reason must be documented when possible)
- Lost to follow-up (every effort must be made to contact the patient; a certified/traceable letter must be sent)
- Study terminated by sponsor
- Site terminated by sponsor
- Pregnancy
- Other reasons

Notification of early patient discontinuation from the study and the reason for discontinuation will be clearly documented on the appropriate eCRF page. Patients who take IP during the study (OL treatment period or the DB treatment period) and who prematurely discontinue from the study, regardless of cause, should be seen for a final assessment. A final assessment will be defined as completion of the evaluations scheduled for Visit 26/ET. If the patient discontinues after IP is taken, the patient is also expected to return for the SFU Visits (Visit 27 and Visit 28) 2 weeks and 4 weeks after completion of the ET visit.

At a minimum, collect the following information when a patient discontinues:

1. The reason the patient discontinued;
2. The date of the last dose of IP from the trial;
3. The date of the last assessment and/or contact. A follow-up contact (telephone or visit) will be arranged as appropriate;
4. (S)AEs;
5. Compliance with the IP administration as specified in this protocol;
6. Final Assessments: Unless there is withdrawal of consent, every effort should be made to ensure that all procedures and evaluations scheduled for Visit 26/ET and subsequently Visit 27 and Visit 28 (SFU Visits) are performed ([Table 2](#), Schedule of Visits and Procedures).

7. Retrieve IP from the patient.

For all patients who discontinue as a result of being lost to follow-up, a determination must be noted in the eCRF as to whether the loss is related to an acute exacerbation of schizophrenia.

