6.7 DOUBLE-BLIND INTENT-TO-TREAT POPULATION

The DB ITT population will consist of all patients who took at least 1 dose of DB IP and had at least 1 post-randomization assessment of the PANSS or CGI-S scores during the DBTP of the study.

Patients will be included in the randomized treatment group for the DB ITT population.

7.0**STUDY PATIENTS****7.1****PATIENT DISPOSITION**

The OLTP starts with the first dose of OLTP and ends with one of the following: the last scheduled assessment at the Visit 13/end of OLTP (Week 18) or early termination (ET) before Visit 13 (Week 18) for patients who do not enter the DBTP; or 1 day before the first dose of DBTP (or the date of the first dose of the DB IP if the last scheduled assessment date in the OLTP is on the date of the first dose of the DBTP) for patients who enter the DBTP.

The DBTP starts with the first day of randomization and ends with the last scheduled assessment at Visit 26 (Week 44) or ET.

The SFU period starts one day after the end of the previous period and ends with the last available assessment. For patients without Visit 27 (Week 46) or Visit 28 (Week 48) assessment, the SFU period would not be derived.

Screen-failure patients (ie, patients screened but not included in the OL Safety Population) and the associated reasons for failure will be tabulated overall for the Screened Population.

The number and percentage of patients in the Screened, OL Safety and OL ITT Populations will be summarized overall and by study center. The number and percentage of patients in the Randomized, DB Safety, and DB ITT Populations will be summarized overall by treatment group and by treatment group and study center.

The number and percentage of patients in the OL Safety Population, who prematurely discontinued from the OLTP, who completed the OLTP, who entered the DBTP, and who entered the SFU period will be summarized overall and by reasons for premature discontinuation as recorded on the respective disposition pages of the electronic case report form (eCRF).

Similarly, the number and percentage of patients in the DB Safety Population who completed the DBTP, who prematurely discontinued from the DBTP, and who entered the SFU period will be summarized overall, by DB treatment group and by reasons for premature discontinuation as recorded on the respective disposition pages of the eCRF. Patients who relapse during the DBTP will also be summarized as completing the study.

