14.0 DETERMINATION OF SAMPLE SIZE

The sample size and power calculations are based on the analysis of time to relapse in the DBTP to compare each cariprazine dose group versus placebo using a log-rank test. The trial will be a fixed follow-up design. Patients are followed from randomization until dropout, relapse or a fixed duration of 26 weeks.

Based on the results from RGH-MD-06, the relapse hazard ratio is assumed to be 0.50, and cumulative relapse rate at Week 26 for the placebo group is 46% (Study RGH-MD-06, 2015). In addition, the cumulative dropout rate due to reasons other than relapse at 26 weeks is assumed to be 20%.

Using these assumptions, a total of approximately 103 relapse events in the DB period need to be observed in order to have 85% power to detect a statistically significant difference between each cariprazine and placebo group, using 2-tailed, log-rank tests at an overall 5% level of significance. The trial should randomize approximately 345 patients, 115 patients each arm, to provide the required number of relapse events. EAST 6.0 was used for sample size and power calculation.

A fixed-sequence procedure will be used for multiple comparisons to control the family-wise Type I error rate at a 0.05 level. First, the cariprazine 4.5 mg/d group will be compared with the placebo group in the primary endpoint; if the test for cariprazine 4.5 mg/d versus placebo is significant at the 0.05 level, then cariprazine 3.0 mg/d arm will be tested versus placebo at 0.05 level.

Assume the screening failure rate is 34%, and approximately 33.3% of patients enrolled into the OLTP will be randomized into the DBTP. Then, approximately 1035 patients will be expected to be enrolled into the OLTP, and approximately 1569 patients are expected to be screened.

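### Non-relapsers who leave the double-blind period without an ET relapse assessment are censored at an undefined discontinuation date, so any gap after their last assessment counts as relapse-free time

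*SAP*

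**What the plan says.** SAP 10.1 defines the endpoint as days from randomization to first relapse within the double-blind treatment period (DBTP). Its censoring rule reads: "Patients who did not meet the above relapse criteria will be censored at the time of completion or discontinuation from the study". Appendix I describes the analysis variable only as time to censoring or relapse.

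SAP 7.1 uses a different anchor for the end of the period: "The DBTP starts with the first day of randomization and ends with the last scheduled assessment at Visit 26 (Week 44) or ET".

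Protocol 8.4.6 includes a relapse assessment at Visit 26/ET. Protocol 8.8 says that patients who took study drug and leave early should have that visit whatever the reason, but makes an exception for withdrawal of consent. For loss to follow-up it requires that "every effort must be made to contact the patient; a certified/traceable letter must be sent". Among the items to collect at discontinuation is "The date of the last assessment and/or contact". Neither document says which date is the discontinuation date for someone who is never seen again.

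SAP Appendix II imputes event times for premature discontinuations from the censoring time to the planned end of follow-up.

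**The concern.** A patient should stay in the risk set only while a relapse could still be recorded. If the censoring date is later than the last point at which status was known, the patient adds time at risk but cannot add an event.

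Two consequences follow. Estimated relapse rates are too low in any arm with such patients. And if one arm loses more of them, the hazard ratio shifts even when the gap per patient is the same in both arms. More loss on cariprazine flatters the drug; more loss on placebo works against it.

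The delta-adjusted and reference-based analyses were added to test the censoring assumption. Because they start at the same date, they leave the gap event-free. The point still matters after the early termination of the study, since SAP Appendix IV keeps the primary efficacy analysis in the abbreviated report.

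**Working it through.** **Inputs from SAP 14.0.** "the relapse hazard ratio is assumed to be 0.50"; placebo relapse 46% at Week 26; 20% dropout for other reasons at 26 weeks, one figure for all arms; 115 patients per arm; about 103 events; 85% power; two-sided 5%; fixed 26-week follow-up. Protocol Table 2 gives visits every 2 weeks.

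**Assumed, because the documents are silent.** Gap length (back to the last 2-weekly visit, 2 weeks, or 4 weeks); share of leavers without an ET visit (none, half, all); unequal dropout of 10% and 30%; constant hazards; dropout independent of relapse; relapses inside the gap unseen.

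**Step 1. Reproduce the plan.** Weekly hazards:
- placebo: −ln(0.54)/26 = 0.02370
- active: half of that, 0.01185, so Week 26 relapse is 1 − √0.54 = 26.5%
- dropout: −ln(0.80)/26 = 0.00858

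Expected events per arm = 115 × λ/(λ+d) × [1 − exp(−26(λ+d))], where λ is the relapse hazard and d the dropout hazard. This gives 48.0 on placebo and 27.5 on each active arm. The total is 48.0 + 2 × 27.5, about 103 as stated (102.9 before rounding). Each placebo comparison has 75.4 events. The Schoenfeld requirement is 4(1.960 + 1.036)²/(ln 0.5)² = 75, and power at 75.4 events is 85.3%. The plan reproduces.

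**Step 2. Effect of the gap.** If a fraction f of leavers have a gap of g weeks, time at risk is inflated by about 1 + d·f·g. The estimated hazard is divided by that factor. The hazard ratio is multiplied by (1 + d_placebo·f·g)/(1 + d_active·f·g).

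*Equal 20% dropout, 4-week gap, no ET visits.* The factor is 1 + 0.00858 × 4 = 1.034 in both arms, so the hazard ratio is unchanged. Week 26 relapse becomes 1 − exp(−26 × 0.02370/1.034) = 44.9% on placebo and 25.8% on active.

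*Dropout 10% placebo, 30% active.* Dropout hazards are −ln(0.90)/26 = 0.00405 and −ln(0.70)/26 = 0.01372. With a 4-week gap and no ET visits the multiplier is 1.0162/1.0549 = 0.963, so 0.50 reads 0.48. With half attending ET it is 1.0081/1.0274 = 0.981, so 0.49. A gap back to the last 2-weekly visit averages 1 week: 1.0041/1.0137 = 0.990.

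**Step 3. Simulation, 400,000 patients per arm.** Each cell compares the SAP rule with censoring at the last assessment.

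| Dropout P/A | Without ET | Gap | Week 26 relapse P/A, SAP rule | Last assessment | HR, SAP rule | HR, last assessment |
|---|---|---|---|---|---|---|
| 20/20 | none | – | 46.1/26.6 | 46.1/26.6 | 0.501 | 0.501 |
| 20/20 | all | last visit | 45.8/26.3 | 46.1/26.5 | 0.498 | 0.498 |
| 20/20 | all | 2 wk | 45.4/26.2 | 46.0/26.6 | 0.502 | 0.502 |
| 20/20 | all | 4 wk | 44.8/25.8 | 45.9/26.5 | 0.502 | 0.501 |
| 10/30 | all | last visit | 46.1/26.3 | 46.2/26.6 | 0.494 | 0.499 |
| 10/30 | all | 4 wk | 45.7/25.3 | 46.3/26.5 | 0.478 | 0.496 |
| 10/30 | half | 4 wk | 45.7/26.0 | 45.9/26.5 | 0.492 | 0.501 |
| 30/10 | all | last visit | 45.7/26.3 | 46.2/26.4 | 0.501 | 0.496 |
| 30/10 | all | 4 wk | 44.5/26.2 | 46.2/26.6 | 0.517 | 0.497 |

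P = placebo, A = active. Within-row ratios agree with Step 2: for 10/30 with a 4-week gap, 0.478/0.496 = 0.964 with no ET visits and 0.492/0.501 = 0.982 with half attending.

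**Step 4. Who is exposed.** At 20% dropout, about 17 placebo and 20 active patients of each 115 are censored early when all attend ET. Only those among them without an ET visit can have a gap.

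**The case against.** The main objection is scope, and it stands. Completers are assessed for relapse at Visit 26, and early leavers are expected at an ET visit that includes the same assessment. If all attend, the rule does nothing. At the plan's single dropout figure the hazard ratio does not move at all. Psychiatric hospitalization, new medication, self-injury or violence may also come to light between visits, and Protocol 8.8 requires sites to record whether a loss to follow-up relates to an acute exacerbation. That shortens the truly unobserved time without closing the gap.

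Three stronger readings are tempting, and the documents do not support them.

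- *Censoring runs into the 4-week safety follow-up.* SAP 4.0 counts that period in the study's length. But Protocol 3.4 has patients complete the study and then be followed for 4 more weeks, Protocol 8.8 places those visits after the ET visit, and SAP 14.0 stops follow-up at 26 weeks. Completion precedes safety follow-up.
- *The lost-to-follow-up date always comes after the contact attempts and letter.* Protocol 8.8 requires a letter but does not tie the date to it. The date of last assessment or contact may be the one used. The date is undefined, not shown to be late.
- *Type I error is materially inflated.* With no true effect, 10%/30% dropout and no ET visits, the tail favouring cariprazine rose from 2.6% to 3.8% (4-week gap) or 5.4% (8 weeks) in 10,000 replicates. A separate run of 6,000 gave two-sided error of 4.8% with no gap, 5.2% and 6.0%. These cases combine zero ET attendance, a threefold dropout imbalance and, at worst, an 8-week gap despite 2-weekly visits. With 15%/25% dropout, half attending ET and a 4-week gap, the one-sided rate was 2.6%, indistinguishable from 2.5%.

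**Conclusion.** The point holds in a limited form. The censoring date is not anchored to known relapse status. For leavers without an ET assessment it is undefined, and any gap counts as relapse-free in both the primary and the sensitivity analyses.

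The size is modest. It is nil if every leaver attends ET. With equal 20% dropout and no ET visits, Week 26 relapse falls by 0.3 to 1.1 points on placebo and 0.2 to 0.7 on active for gaps up to 4 weeks, with no change in hazard ratio. With 10%/30% dropout the hazard ratio moves about 1% to 4% if none attend ET and about half that if half attend, in either direction.

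These figures rest on the assumed gaps, ET attendance and dropout splits, and on dropout unrelated to relapse. If relapse itself drives dropout the bias could be larger, but that is informative censoring. The 103 events and 345 patients need no change. The amendment is worth considering; it is not a condition for a valid primary analysis.

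**What to change.** In SAP 10.1, censor patients without relapse at the last visit in the DBTP, as Section 7.1 defines that period, at which the relapse criteria were assessed. If a later documented contact established relapse status, use that contact. In no case censor after the end of the DBTP. Start the Appendix II imputation from the same date. Keep the present rule as a sensitivity analysis if wanted, and for that purpose state which date counts as discontinuation for a patient lost to follow-up.

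The cost is one SAP sentence and one derived date. Protocol 8.8 already collects the date of last assessment or contact, though the derivation must separate contacts that established relapse status from those that did not. Slightly less follow-up time is counted. The change does not cure informative dropout, which remains the task of the two imputation analyses.

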10.2 SECONDARY EFFICACY PARAMETER

Not applicable.

10.3 ADDITIONAL EFFICACY PARAMETERS

The additional efficacy parameters will include the following at scheduled postbaseline visits:

- Change from baseline in the PANSS total score
- Change from baseline in PANSS positive subscale score
- Change from baseline in PANSS negative subscale score
- Change from baseline in PANSS factor score for positive symptoms
- Change from baseline in PANSS factor score for negative symptoms
- Percentage response (PANSS improvement \geq 30%)
- Change from baseline in the CGI-S score
- Clinical Global Impressions—Improvement (CGI-I) score

- Change from baseline in the Brief Assessment of Cognition in Schizophrenia scale (BACS) individual subtest scores
- Change from baseline in BACS composite score Z score
- Change from baseline in the BACS composite T score
- Change from baseline in personal and social performance (PSP) score and sub-domain scores

For the continuous endpoints, the change from baseline refers to the change from OL baseline during the OLTP, and the change from DB baseline during the DBTP, unless stated otherwise. For CGI-I, the OL baseline CGI-S value will be used as the baseline variable.

Descriptive statistics for additional quantitative parameters will be provided by visit for the OL ITT population and the DB ITT population using both last-observation-carried forward (LOCF) and observed cases (OC) approaches. LOCF approach will be used to impute missing postbaseline values. Imputation of missing values will be done for the OLTP and the DBTP separately.

For the DBTP, the continuous variables (change from DB baseline) will be analyzed by using a mixed-effects model for repeated measures (MMRM) with treatment group, country, visit, and treatment group-by-visit interaction as fixed effects and the baseline value and baseline-by-visit interaction as the covariates. An unstructured covariance matrix will be used. The Kenward-Roger approximation ([Kenward and Roger, 1997](#)) will be used to estimate denominator degrees of freedom. The analysis will be performed based on post-DB baseline scores using only the OC without imputation of missing values. Least squares mean and their standard errors based on the MMRM analysis will be plotted by treatment group and visit.

Within regions, countries will be ranked on number of patients that are part of the ITT population and lowest ranked countries will be pooled (sequentially, ie, a new ranking is made after each step) until the smallest pooled country has reached at least 2 patients in each arm.

Additional categorical efficacy parameters will be analyzed in the following way:

Rates for categorical parameters (response) will be reported by treatment group and by visit for both the OLTP and the DBTP (with LOCF imputation). For the DBTP, logistic regression model (with LOCF imputation) will be used to model the probability of a response or the probability of a response as a function of a treatment group and the corresponding baseline score as explanatory variables.

